6.2 Study Visits

For each patient, a maximum of 10 scheduled visits will be performed:

- Visit 1 at Day -14 (Day -21 to -12): Screening: The screening examination to determine patient eligibility can take place anytime within this time period.

- Visit 2 at Day 1: Baseline (12-21 days after Visit 1)
- Visit 3 at Day 15 ± 2 days
- Visit 4 at Day 29 ± 2 days
- Visit 5 at Day 57 ± 7 days
- Visit 6 at Day 85 ± 7 days

For the patients who are assigned into the 12-week Primary Period

- Visit 6.5 (post-dose) at Day 99 ± 7 days (at least 14 days after the last dose of study medication)

For the patients who are assigned into the 52-week Overall Period (with the 40-week Extension Period):

- Visit 7 at Day 169 ± 7 days
- Visit 8 at Day 253 ± 7 days
- Visit 9 at Day 365 ± 7 days
- Visit 10 (post-dose) at Day 379 ± 7 days (at least 14 days after the last dose of study medication)

The procedures and assessments to be performed at each visit are indicated in [Table 1](#).

6.3 Compliance with The Protocol

The Investigator must agree to implement the study protocol as written and adhere to the guidelines given in the Investigator's Statement, which will be signed prior to the start of the study. The study will be performed in accordance with HIPAA, Declaration of Helsinki, International Council for Harmonisation (ICH) Good Clinical Practice (GCP) guidelines, local laws, FDA GCP regulations (21 Code of Federal Regulations [CFR] Parts 11, 50, 54, 56, and 312), and other applicable guidance documents.

If the Investigator considers enrolling a patient that does not meet all inclusion or exclusion criteria, an exemption must be requested from the sponsor's medical monitor prior to patient enrollment. The justification for the exemption must be documented by the Investigator. The approval or rejection of the exemption must be documented by the sponsor's medical monitor prior to the patient's enrollment or screen failure.

Protocol non-compliance must be reported to the sponsor or its representatives. Each deviation and the reason for its occurrence must be documented. The sponsor retains the right to require the withdrawal of any patient who violates the protocol.

6.4 Termination of the Study

If, in the opinion of the Investigator, the clinical observations in the study suggest that it may be unwise to continue, the study may be terminated after consultation with the sponsor. A written statement fully documenting the reason(s) for the termination will be provided to the sponsor. In addition, the sponsor may terminate the study at any time.

If it becomes apparent that patient enrollment is unsatisfactory with respect to quality or quantity, or data recording is inaccurate or incomplete on a chronic basis, the sponsor has the right to terminate the study and remove all study materials from the investigational site. A written statement will be provided to the Investigator, the Institutional Review Board/Independent Ethics Committee/Research Ethics Committee (IRB/IEC/REC), and regulatory authorities, if required. In the event of any serious or non-serious AEs having occurred at a site, all documentation relating to the event(s) must be obtained.

7.0 STUDY MEDICATION

7.1 Description of Study Medication

K-161 ophthalmic solution is formulated as a [REDACTED] for topical ophthalmic administration. The drug product is supplied in [REDACTED] suitable for administration directly onto the eye. A placebo to match sterile product (vehicle) is provided using the same excipient formulation as the active K-161 product.

Each drug product contains the following excipients: [REDACTED]
[REDACTED]

7.2 Drug Packaging

The drug product is packaged into [REDACTED]
that are sealed within [REDACTED] and ultimately
contained in carton kits [REDACTED]. Each patient will receive 1 kit at
Visit 1; 4 kits at Visit 2, 6, and 7; and 6 kits at Visit 8, as applicable, to provide a
sufficient supply of run-in and randomized study drug.

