Vehicle Run-In Dispensation	X										
Vehicle Run-In Instillation	X										
Vehicle Run-in Collection and Accountability		X									
Determination/assignment of the study eye		X									
Randomization		X									
Study Drug Dispensation		X				X ^d	X ^d	X ^d			
Study Drug Instillation		X		X	X	X ^d	X ^d	X ^d			
Study Drug Collection and Accountability				X ^e	X ^e	X	X ^d	X ^d	X ^d		
Fluorescein Staining Scoring	X	X		X	X	X	X	X	X		
VAS	X	X		X	X	X	X	X	X		
TFBUT	X	X		X	X	X	X	X	X		
Schirmer's Test	X	X		X	X	X	X	X	X		

ASSESSMENTS PERFORMED	STUDY PERIOD										Post-dose Assessments	
	Screening /Run-in Period	Days of Dosing and Assessments										
		52-week Overall Period										
		12-week Primary Period					40-week Extension Period					
Visit 1 Day -14 (Day -21 to -12)	Visit 2 Day 1 (Baseline)	Visit 3 Day 15 ± 2 (Remote) ^a	Visit 4 Day 29 ± 2	Visit 5 Day 57 ± 7	Visit 6 Day 85 ± 7	Visit 7 ^b Day 169 ± 7	Visit 8 ^b Day 253 ± 7	Visit 9 ^b Day 365 ± 7	Visit 6.5 ^b Day 99 ± 7 ^c or Visit 10 ^b Day 379 ± 7 ^c			
Adverse Event Collection	X	X	X	X	X	X	X	X	X	X		
Systemic Clinical Evaluation		X				X			X			
Clinical Laboratory Measurement	X					X			X			
Exit Patient from Study										X		

HIPAA=Health Insurance

Portability and Accountability Act; OSDI=Ocular Surface Disease Index; TFBUT=tear film break-up time; VAS=Visual analog scale.

Note: The visit schedule will always be calculated from randomization visit date (Visit 2).

- a. Visit 3 will be a remote visit.
- b. Only first 120 patients of each arm, approximate total 240 patients, will proceed to Visit 7 (Day 169) and following visits. Other patients will proceed to Visit 6.5 (Day 99) for post-dose assessments.
- c. Post-dose assessments will be performed at least 14 days after the last dose of study medication.
- d. Only patients in the Extension Period will be dispensed and instilled with the study drugs and will be examined for [REDACTED]

e. Patients will be instructed to bring all [REDACTED] to assess dosing compliance, however, only the used [REDACTED] will be collected and the [REDACTED] will be returned to patients at Visit 4 and Visit 5.

f. [REDACTED]

g. [REDACTED]

h. [REDACTED]

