12. TFBUT

13. Corneal and conjunctival fluorescein staining scoring

16. Schirmer's test

[REDACTED] after completing the above steps: The following procedures will be conducted for eligible patients only.

19. Determination/assignment of the study eye
20. Randomization
21. Study drug kit dispensation: All patients meeting all other screening eligibility criteria at the end of Visit 2 will be randomized to 1 of 2 treatment groups utilizing the Interactive Web Response System (IWRS) system. Patients will receive their assigned study drug kit with sufficient supply to last until the day before Visit 6.

26. Patient instructions dispensation

27. AE collection

28. Patients will be scheduled for Visit 3 (remote visit).

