7.5.1 Drug Administration

Patients will be instructed to administer study drug [REDACTED]. If missed, the patient must not administer the eye drop if the next dosing is in less than 2 hours. At every study visit (except remote), all patients must visit their study sites without administering any topical ophthalmic preparations, including study drug, and must not administer topical ophthalmic preparations until all required examinations are finished.

Patients, sponsor, CRO, and site personnel will be masked to treatment assignment. Patients will be instructed not to discuss their assigned dosing regimen or any perceived treatment effects with other study participants.

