Kowa Research Institute, Inc.

K-161-3.01

A Phase 3, Prospective, Double-masked, Randomized, Multi-center, Vehicle-controlled, Parallel-group, 12-week Administration and 40-week Extension Study Confirming the Efficacy and Safety of K-161 Ophthalmic Solution for the Treatment of Moderate to Severe Dry Eye Disease

NCT05403827

2023-10-03

[figure not shown]
[figure not shown]
Addendum to Statistical Analysis Plan

Version 1.0

[figure not shown]
Prepared by:

Signature Page:

Kowa Research Institute, Inc.

Kowa Research Institute, Inc

Introduction:

The objective of this Statistical Analysis Plan (SAP) addendum is to provide modifications and corrections to the final *K-161-3.01* SAP, dated May 24, 2023.

List of Modifications/Corrections to the final *K-161-3.01* SAP Dated May 24, 2023:

1. Change to per protocol set (PPS) defined in SAP Section 4.4.2

PPS is redefined to exclude subjects with major protocol deviations (PDs) related to primary and key secondary endpoints, rather than all major PDs as defined by the PD Guidance Plan. These major PDs were identified during blinded data review. This change is made to have a more meaningful PPS focusing on primary and key secondary endpoints and to avoid exclusion of subjects with deviations that do not impact the primary or key secondary efficacy assessments.

2. Presentation for actual treatment

The definition of actual treatment for subjects who received incorrect treatment different from their randomized treatment was reaffirmed during the data review meeting. In the safety analyses, a subject will be classified as part of the K-161 group in accordance with SAP Sections 4.4.3 and 4.4.5 if they were initially assigned to the placebo group but received at least one kit of the K-161 treatment. For other treatment errors, the actual treatment group will match the randomized treatment unless a subject was initially allocated to the K-161 group but received placebo treatment kits throughout the study. These decisions are based on the understanding that one kit is used for 3 weeks of treatment.

3. Modifying Race classifications

Race (see SAP Section 6.1) will be handled according to CDISC SDTM terminology like below.

Race as collected	CDISC SDTM terminology
White	White
Black or African American	Black or African American
American Indian or Alaska Native	American Indian or Alaska Native
Asian Indian	
Chinese	
Filipino	
Japanese	Asian
Korean	
Vietnamese	
Other Asian	
Native Hawaiian	

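### Does the four-kit supply from Visit 2 run out before a Visit 6 held late in its ±7-day window?

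*Protocol*

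**What the plan says.** Protocol Section 7.2 gives one kit at Visit 1 for the run-in and then "4 kits at Visit 2, 6, and 7; and 6 kits at Visit 8", and describes this as enough for both run-in and randomized treatment. The description of what a kit holds is redacted there. Section 5.1.1.2 says patients leave Visit 2 with a kit supply "sufficient supply to last until the day before Visit 6". Section 6.2 schedules "Visit 6 at Day 85 ± 7 days", and the note to Table 1 counts all visit days from Visit 2. Table 1 shows study drug dispensed at Visits 2, 6, 7 and 8 only. At Visits 4 and 5 there is accountability but no new supply.

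The only kit duration in the documents is in item 2 of the SAP addendum: "one kit is used for 3 weeks of treatment". It is given there to explain how patients who received wrong kits are classified for the safety analyses.

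Section 7.6 sets compliance limits of 80% and 125%, applied to each visit interval as well as to the 12-week, 40-week and 52-week periods.

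**The concern.** Read together, these sections seem not to fit. Four kits at three weeks each end on Day 84, while a permitted Visit 6 can fall up to a week after Day 85 with no resupply in between. A late visit inside the window is not a deviation. Running out of drug is also not among the intercurrent events in Section 10.2, which lists only discontinuation for an adverse event or for lack of efficacy.

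Both primary endpoints are read at Visit 6. If some patients were assessed after several days without drug, and if the effect fades over that time, the difference between K-161 and vehicle would shrink. The sample size has almost no slack to absorb this.

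**Working it through.** **Kit counts at nominal visit days.** Inputs: 21 days per kit (addendum item 2) and the visit days and windows (Section 6.2). Patients must "visit their study sites without administering any topical ophthalmic preparations, including study drug" (Section 7.5.1), so the last dose needed falls on the day before the visit. Dosing days therefore equal the difference between visit days, and kits needed = dosing days ÷ 21, rounded up.

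| Interval | Kits given | Supply at 21 days/kit | Nominal need | Longest permitted need | Shortfall at longest |
|---|---|---|---|---|---|
| Run-in | 1 | 21 | 14 | 21 | 0 |
| Visit 2 to 6 | 4 | 84 | 84 | 91 (Day 1 to 92) | 7 |
| Visit 6 to 7 | 4 | 84 | 84 | 98 (Day 78 to 176) | 14 |
| Visit 7 to 8 | 4 | 84 | 84 | 98 (Day 162 to 260) | 14 |
| Visit 8 to 9 | 6 | 126 | 112 | 126 (Day 246 to 372) | 0 |

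At nominal days 21 days per kit reproduces every count: 84/21 = 4 three times, 112/21 = 5.33 rounded up to 6, and one kit for the run-in. With exactly 21 days per kit, the gap before Visit 6 is 0 for visits on Day 78 to 85, then rises from 1 day on Day 86 to 7 days on Day 92.

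**What capacity would close it.** For Visit 6: 91/4 = 22.75 days per kit, which is 1.75 days or about 8% above 21. At 22 days per kit the gap on Day 92 is 91 − 88 = 3 days. To cover every window: 98/4 = 24.5 days per kit. Six kits would still be the smallest sufficient number at Visit 8 as long as five fall short of 126 days, that is, below 126/5 = 25.2. So the same counts fit 21 days per kit at nominal dates, and equally 24.5 to just under 25.2 days per kit covering every window. The counts do not settle capacity. The match of six kits to 126 days may simply be rounding up from 5.33.

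**Whether compliance would show it.** Over the whole primary period, 84/91 = 92%, which passes. Section 7.6 also applies the limit to each visit interval. With exactly 84 days of supply and full adherence, Visit 5 to 6 compliance is (85 − V5)/(V6 − V5), where V5 and V6 are the visit days:

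- Visit 6 on Day 92: 28/35 = 80.0% if Visit 5 is on Day 57; 27/34 = 79.4% on Day 58; 21/28 = 75% on Day 64. A 7-day gap is flagged when Visit 5 is on Day 58 to 64.
- Visit 6 on Day 91: 24/30 = 80.0% on Day 61; 23/29 = 79.3% on Day 62. A 6-day gap is flagged when Visit 5 is on Day 62 to 64.
- Visit 6 on Day 90: at worst 21/26 = 80.8%. Gaps of 5 days or fewer pass.

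**Effect on power.** From Section 10.1, the planned difference is 0.92 × (10.0 − 3.6) = 5.888. The K-161 arm's variance, allowing for its two patterns, is 431.2 + 0.92 × 0.08 × 6.4² = 434.2. With 310 per arm, SE = √((431.2 + 434.2)/310) = 1.671, and power is Φ(5.888/1.671 − 2.241) = 90%, as planned. To go further one must assume both the share seen after Day 85 and the fraction of effect lost in those patients. Power for fades of 10% / 25% / 50%:

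- Visit days uniform over Day 78 to 92, so 7/15 = 47% late: 87% / 81% / 68%.
- 20% late: 89% / 87% / 82%.

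None of these shares or fades comes from the documents, and all the figures also require exactly 21 days per kit and full adherence. A patient who uses 84/91 = 92% of doses makes 84 days of supply last 91 days.

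**The case for a change.** The best argument for acting is that three weeks is the only kit duration in the documents, that the sponsor relied on it for a classification rule, and that it reproduces every kit count at nominal dates. Overage is possible, but nothing visible states it. The assurance in Section 5.1.1.2 is one side of the apparent conflict and cannot by itself resolve it. No resupply is described before Visit 6, most short gaps would pass the compliance rule, and 310 per arm only just reaches 90% power. The analysis part of a remedy would be cheap: compute days from end of supply to Visit 6, and repeat the primary analysis in patients whose supply lasted.

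Part of this stands. On the visible figures Sections 5.1.1.2, 6.2 and 7.2 and the addendum do not plainly agree, and gaps of up to 5 days would not be flagged. The rest does not carry the conclusion. A remark about use, made for another purpose, is not a fill specification, and redacted contents cannot be read as having no overage. The compliance rule would catch some of the longest gaps. The 14-day figures need adjacent visits at opposite ends of their windows and concern the extension, not the primary endpoints.

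The added table would also gain little. The primary analysis compares patients as randomized, regardless of adherence, and uses measurements taken after treatment stops for an adverse event or lack of efficacy. A subset chosen by supply and visit timing would not replace it.

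**Conclusion.** No change to the plan. The tension is a missing detail: the public documents do not show how many days a kit can cover. If capacity is at least 22.75 days, the Visit 2 supply reaches the end of the Visit 6 window as Section 5.1.1.2 says. If it is exactly 21 days, the gap is 1 to 7 days for fully adherent patients seen on Day 86 to 92, and none for anyone seen by Day 85. The sections can be reconciled by confirming from the unredacted packaging details whether kit capacity covers the upper limit of the windows; this needs no change to the design or the analysis.

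The effect on the primary endpoints cannot be quantified from the documents. If a gap did occur and the effect faded, the comparison would be pulled toward no difference, so it could not create a false positive, and the treatment-policy analysis would stay valid. These conclusions rest on the visible text only: kit contents are redacted, and the main SAP of May 24, 2023, including its compliance section, is not among the documents, so what it already does about exposure timing is unknown.

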7.3 Drug Labeling

Study drug will be labeled according to country/state/province specific requirements,
with the following information:

1. Name and address of sponsor (e.g., KRI)
2. Drug name, dosage form, and quantity of dosage units
3. Lot number (as required)
4. "Caution - New Drug - Limited by Federal (US) Law to Investigational Use"
5. The storage conditions
6. "Keep out of reach of children"
7. Expiration date (as required)

7.4 Drug Storage

The study drug must be stored in a secure area accessible only to the Investigator and
his/her designees. K-161 must be stored [REDACTED]
[REDACTED] as indicated on
the product label.

7.5 Dispensing and Administration of Treatment

All arms will be double-masked. The treatments administered will be:

- [REDACTED] K-161; [REDACTED]
- Placebo ophthalmic solution (vehicle); [REDACTED]

Labeling and packaging for the run-in period will be identical to those for the double-masked treatment periods. The run-in drops (vehicle) will be single-masked for patients.

7.5.1 Drug Administration

Patients will be instructed to administer study drug [REDACTED]. If missed, the patient must not administer the eye drop if the next dosing is in less than 2 hours. At every study visit (except remote), all patients must visit their study sites without administering any topical ophthalmic preparations, including study drug, and must not administer topical ophthalmic preparations until all required examinations are finished.

Patients, sponsor, CRO, and site personnel will be masked to treatment assignment. Patients will be instructed not to discuss their assigned dosing regimen or any perceived treatment effects with other study participants.

7.5.2 Diet or Physical Exercise

No special diets or activity restrictions are required for this study. Patients are asked not to change their personal routines (e.g., the use of eyelid scrubs and warm compresses) throughout the study.

7.6 Compliance with Dispensed Study Drug Dosing Regimen

Patients will be given written instructions, instructed on proper instillation, and instructed on proper storage of the study drug at the end of every study visit except for the end of treatment period and post-dose assessments (Visit 6.5 and 10). To assess dosing compliance, patients will be instructed to bring all [REDACTED] at their next visit throughout the study duration. The patient [REDACTED] will be collected at Visit 2 and Visit 6 for all patients and from Visit 7 to Visit 9 for patients entering the 40-week Extension Period. At Visit 4 and Visit 5, only the [REDACTED] will be collected and the [REDACTED] will be returned to patients. Dosing compliance will be based on the [REDACTED]. If the patient is less than 80% or more than 125% compliant during each visit interval, 12-week Primary Period, 40-week Extension Period, and 52-week Overall Period, with dosing based on the expected number of [REDACTED], then the patient will be deemed non-compliant and a dosing deviation should be recorded in the source document. The Investigator will use these guidelines to determine patient study compliance and deviation.

7.7 Drug Accountability

The study drug is to only be dispensed by the PI or his/her named sub-Investigator(s), and is to only be used in accordance with this protocol. The study drug must only be distributed to patients properly qualified as described in this protocol to receive study drug.

The Investigator must keep an accurate account of the study drug received from the supplier. This includes the amount of study drug dispensed to patients, amount of study drug returned to the Investigator by the patients, and the amount returned or disposed upon the completion of the study. A detailed inventory must be completed for the study drug.

7.8 Procedure for Unmasking

As needed, the randomization code may be broken by the Investigator to manage an urgent medical safety event. If possible, the medical monitor should be contacted to discuss the case before the code is broken.

If it becomes necessary to unmask treatment information during the study, the reason for unmasking must be documented in the eCRF. If the medical monitor cannot be notified prior to unmasking, the Investigator must contact the medical monitor promptly and explain the reason for the premature unmasking (e.g., unmasking due to an SAE).

Planned analyses at Day 85 including the primary analyses will be performed by unmasked team not involved in the conduct of the study once all patient data until Day 85 are obtained in a fashion to protect the masking of the patients who will be followed in the 40-week Extension Period.

8.0 CONCOMITANT MEDICATION

The Investigator must record the use of all concomitant medications and any historical use of [REDACTED] before Visit 1, both dispensed and OTC, in the eCRF along with the reason the medication was taken. This includes drugs used on a chronic and as-needed basis. Patients must be discouraged from starting any new medication, both dispensed and OTC, without consulting the Investigator, unless the new medication is required for emergency use.

8.1 General Considerations

Concurrent enrollment in another investigational drug or medical device study is not permitted.

8.2 Prohibited Medication

Disallowed medications/treatments during the study are outlined in the exclusion criteria (Section 4.2).

8.3 Permitted Medication and Rescue Therapy

Contact lenses are allowed only during the 40-week Extension Period (except for study visit days before all visit assessments are completed). Contact lenses should be removed prior to the administration of study drug and may be reinserted at least 15 minutes following administration. If a patient is using another prescription eye drop in combination with the study medication, the concomitant use of contact lenses is not recommended for the duration of such combination therapy.

The following medications are permitted as long as the dosage is stable:

- Systemic tetracycline compounds (e.g., tetracycline, doxycycline, or minocycline), macrolides (e.g., azithromycin): for at least 30 days prior to Visit 1 and dose will remain stable until the end of the 12-week Primary Period
- Any medication (topical and systemic) known to cause ocular drying, such as systemic anticholinergic medications (e.g., atropine, homatropine), antidepressants and antipsychotic agents, statins, diuretics, beta-blockers, NSAIDs: for at least 30 days prior to Visit 1 and dose will remain stable until the end of the 12-week Primary Period
 - Episodic use of anticholinergic drops for eye examination and episodic use of systemic NSAIDs are allowed during the study except for within 2 days prior to any study visit.
- Omega-3 fatty acid supplements in doses above 3000 mg/day, oral hormonal contraceptives, hormone replacement therapy for menopause: for 12 weeks prior to Visit 1 and dose will remain stable until the end of the 12-week Primary Period. Omega-3 fatty acid supplements in doses equal to or below 3000 mg/day are permitted.

Any prohibited and restricted medications, devices, and procedures indicated for dry eye disease are permitted as “rescue therapy” after all assessments are completed at Visit 6 (except for study visit days before all visit assessments are completed) (Table 1).

Especially, [REDACTED] will be summarized as described in Section 5.2.10. All other prohibited medications, other than isotretinoin, systemic [REDACTED], and restricted medications, devices, and procedures are permitted as “permitted therapy” after all assessments are completed at Visit 6 (except for study visit days before all visit assessments are completed). If more than one topical ophthalmic medicinal product is being used, the medicinal products must be administered at least 15 minutes apart.

Any non-emergent ocular surgical procedure is prohibited until the end of the 12-week Primary Period. However, if the patient’s condition necessitates a surgical ocular procedure during the study, the patient may undergo rescue ophthalmic surgery. In this case, the use of study medication should be interrupted in the eye undergoing the procedure until resolution or stabilization of this condition and full recovery after surgery as determined by the Investigator. The decision to interrupt or restart the study medication for a specific ocular procedure/condition should be based on the best clinical judgment of the Investigator and preferably after consultation with the medical monitor.

